## **VI. BIOSTATISTICAL ANALYSIS**

Primary outcomes are acute and late complications following proton beam irradiation to the tumor or tumor bed. Late complications are defined as the delayed effects attributable to radiation which occur > 90 days following completion of radiation, while acute side effects are those occurring during radiotherapy or up to 90 days after the last dose. Allowing for 5% inflation for unevaluable patients due to ineligibility or early dropout, the revised accrual goal is a total of 115 patients with a minimum follow-up of another 2

years following the patient enrollment for observing the late complications of proton beam irradiation.

The goal of utilizing protons is an improvement in the historical complication rate, which varies by site and type of complication. The literature for parameningeal or other head and neck rhabdomyosarcomas has reported endocrine effects occurring in 50-100% and impaired orbital function in 70-100% of patients (23-27). For children treated for pelvic tumors, late effects were significantly higher among patients treated, ranging from 54% to 77% (28). Across all anatomic sites, the likelihood of one or more reported late effects has been approximately 70% or more among those who received conventional radiation. Among a total of 110 patients, the probability is 81% that 70 or fewer of them will develop any late effect if the overall complication rate is truly decreased to 60% with the use of protons. The decision rule is associated with only 9% probability if the underlying rate were truly similar to the 70% historical rate observed with conventional radiation.

Due to a difference in the radiation doses used for treating patients with different tumor characteristics (typical doses are 36 Gy, 41.4 Gy, 45 Gy and 50.4 Gy), the outcomes will be analyzed according to dose group,  $\leq$  45 Gy and  $\geq$  45 Gy. Data on the enrolled patients shows a 1:4 ratio in the distribution of patients receiving low versus intermediate radiation doses. Constitutional symptoms, namely fatigue and malaise, as well as skin reactions in the radiation port will be analyzed according to dose group.

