As rhabdomyosarcoma may occur at almost any site, many of the side effects will be determined by the range of tumor location. Thus analysis of tissue-specific toxicities has depended typically on relatively small patient numbers and was limited generally to descriptive statistics. Moreover, subgroup analysis of acute symptoms may be confounded by the type of concurrent chemotherapy. Accrual has been increased to obtain reasonable precision for the estimation of tissue-specific toxicities associated with the most common tumor sites, especially late effects arising during long-term follow-up. Patients will not be evaluable for late effects following treatment failure in local, regional and/or metastatic sites, development of a secondary malignancy or death due to any cause. In particular, projection of the current patient distribution indicates the increased accrual will comprise 56 patients with parameningeal tumors and 24 patients with orbital sarcomas. These expected numbers are associated with 95% exact confidence intervals of maximal width  $\pm$  14% and  $\pm$  22%, respectively. The corresponding numbers evaluable for late effects are projected to be 42 and 18 patients based on the five-year event-free survival of 69% observed among the first 57 protocol patients. The maximal interval widths are  $\pm$  17% and  $\pm$  25%, respectively, at five years following proton radiotherapy. We also expect to enroll 3-6 patients with each of the rare tumor sites (non-parameningeal head and neck, trunk, prostate/bladder, extremity, perineal/anal and liver/biliary tract regions).

All toxicity grading will be coded according to the COG/RTOG scales provided in the appendices. Toxicities and events not listed in these scales will be graded according to the Common Terminology Criteria for Adverse Events (CTCAE), Version 3.0. Many patients are expected to be co-enrolled on COG protocols comparing chemotherapy

regimens. Since interim analysis will be performed on the parent COG protocols and any action taken will impact directly on the proton protocol, no formal sequential monitoring of efficacy is planned within this protocol.

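### The projected 42 and 18 patients evaluable for late effects do not follow from the cited 69% event-free survival (about 39 and 17), and the printed ±17% and ±25% are not the exact 95% widths for 42 and 18

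*Combined protocol and SAP*

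**What the plan says.** All the figures are in Section VI (Biostatistical Analysis) of the combined protocol and SAP. From the current patient distribution the plan projects that "the increased accrual will comprise 56 patients with parameningeal tumors and 24 patients with orbital sarcomas". It adds: "These expected numbers are associated with 95% exact confidence intervals of maximal width" ±14% and ±22% respectively.

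It then allows for patients who drop out of the late-effects assessment. The rule is that "Patients will not be evaluable for late effects following treatment failure in local, regional and/or metastatic sites", and likewise after a second malignancy or death. On that basis: "The corresponding numbers evaluable for late effects are projected to be 42 and 18 patients based on the five-year event-free survival of 69" per cent. The rate is described as the "five-year event-free survival of 69% observed among the first 57 protocol patients". The matching maximal widths are given as ±17% and ±25%, "respectively, at five years following proton radiotherapy".

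The only other attrition figure in the section concerns total accrual: "Allowing for 5% inflation for unevaluable patients due to ineligibility or early dropout".

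**The concern.** The text names one input for the evaluable counts, 69%, and that input does not give them. Both counts are too high by the same factor, so rounding is not the cause. The widths that follow then need checking against the counts they sit beside, and they do not match those counts.

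Late complications are a primary outcome. Section VI gives precision for toxicity at the commonest tumour sites, late effects above all, as the reason for raising accrual. These sentences are the numerical support for that reason. As printed, the rate, the counts and the widths cannot all be true together, and a reader cannot tell which counts or which interval definition the planned precision rests on. Anyone who later compares achieved with planned evaluable numbers would be using an overstated target.

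**Working it through.** **Inputs (all Section VI).** Projected enrolment 56 and 24; five-year event-free survival 69%; printed evaluable counts 42 and 18; printed widths ±14% and ±22% (enrolled) and ±17% and ±25% (evaluable); 5% allowance for unevaluable patients.

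**Counts.** Evaluable number = enrolled number × five-year event-free survival.

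- Parameningeal: 56 × 0.69 = 38.64, about 39 (printed 42; difference 3.4).
- Orbital: 24 × 0.69 = 16.56, about 17 (printed 18; difference 1.4).
- Implied rate: 42/56 = 0.75 and 18/24 = 0.75, both exact.

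Two other routes to the printed counts were tried:

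- Adding the 5% allowance: 56 × 0.69 × 0.95 = 36.7 and 24 × 0.69 × 0.95 = 15.7, which is further away.
- Scaling up by 115/110 (accrual goal over the number in the decision rule): 56 × (115/110) × 0.69 = 40.4 and 24 × (115/110) × 0.69 = 17.3, still short.

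**Widths.** The plan calls for exact 95% intervals, taken here as Clopper-Pearson. For x events in n patients the limits are:

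- lower L = 2.5th percentile of Beta(x, n − x + 1)
- upper U = 97.5th percentile of Beta(x + 1, n − x)

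These intervals are asymmetric and the plan does not define ±, so two readings were computed, each maximised over x = 0 to n:

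- larger distance = max(x/n − L, U − x/n)
- half-width = (U − L)/2

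| n | Basis | Printed ± | Larger distance | Half-width |
|---|---|---|---|---|
| 56 | enrolled | 14% | 13.96% | 13.66% |
| 24 | enrolled | 22% | 21.99% | 20.88% |
| 42 | printed evaluable | 17% | 16.27% | 15.81% |
| 18 | printed evaluable | 25% | 25.70% | 23.98% |
| 39 | 69%, rounded | (17%) | 16.92% | 16.40% |
| 17 | 69%, rounded | (25%) | 26.55% | 24.60% |
| 38 | 69%, rounded down | (17%) | 17.16% | 16.62% |
| 16 | 69%, rounded down | (25%) | 27.41% | 25.35% |

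Reading the table:

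- The enrolled pair, ±14% and ±22%, reproduces by larger distance. Half-width would print 14% and 21%.
- For 42 and 18, larger distance rounds to 16% and 26%, and half-width to 16% and 24%. Neither gives 17% and 25%.
- For 39 and 17, larger distance gives all the printed widths except ±25%. Half-width gives ±14% and ±25% but misses ±22% and ±17%.
- For 38 and 16, half-width rounds to 17% and 25%, but the same reading still misses ±22% for n = 24.

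Other interval formulas do not rescue 42 and 18: at a proportion of one half, Wald gives 15.1% and 23.1%, continuity-corrected Wald 16.3% and 25.9%, and Wilson 14.5% and 21.0%.

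**The case against.** The best defence is that only the counts are wrong and the printed widths are sound. A third common planning reading takes the larger distance to a limit at the observed proportion nearest 50%. For n = 39 (x = 19) that is 16.50%, and for n = 17 (x = 8) it is 25.13%, so ±17% and ±25% both reproduce for exactly the counts that 69% implies. On this view, correcting two numbers is enough, and restating the widths is a matter of clarity.

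Much of this stands. It strengthens the inference that the second pair of widths was computed at 69% and that 42 and 18 came from elsewhere. It does not clear the text, however. The same reading gives 20.9% for n = 24 against the printed 22%, and 15.8% and 24.0% for 42 and 18. No reading tried reproduces all four printed widths, and the widths do not belong to the counts they are attached to.

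It is also fair to say that the figures are projections. The 69% comes from only 57 patients across all sites, a difference of three and one patients is modest beside that uncertainty, and the 18 taken alone is only 1.4 patients off. The plan sets no precision threshold and describes site-specific analyses as generally descriptive. These points limit the weight of the finding. They do not explain a shared 75% factor beside a stated 69%.

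**Conclusion.** The passage is wrong as written, and the error is minor. At 69% the evaluable counts are about 39 and 17, so the plan overstates them by three parameningeal patients and one orbital patient.

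On precision:

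- For 42, the printed ±17% is about one point wider than the exact value under either tabulated reading.
- For 18, the printed ±25% falls between the two readings (24.0% and 25.7%) and matches neither after rounding.
- For 39, ±17% is right by larger distance and slightly conservative by half-width.
- For 17, ±25% is right by half-width and about 1.5 points too narrow by larger distance.

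The 110-patient decision rule in Section VI and the suspension rule in Section IX do not use these figures.

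This rests on three assumptions: 56 and 24 are taken as given; the overall 69% applies to both sites, since no site-specific rate is stated; and exact means Clopper-Pearson. That the widths already reflect 69% is an inference; the documents do not say so.

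**What to change.** Change two sentences in Section VI.

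1. Replace 42 and 18 with 39 and 17, showing 56 × 0.69 and 24 × 0.69. If a 75% rate was intended, state it and its source in place of 69%.
2. Name the interval (Clopper-Pearson) and one definition of ±, and give all four widths under it:
   - For 56, 24, 39 and 17, by larger distance: ±14%, ±22%, ±17% and ±27%.
   - For the same counts, by half-width: ±14%, ±21%, ±16% and ±25%.
   - If 75% is justified and 42 and 18 stay, the second pair becomes ±16% and ±26% by larger distance, or ±16% and ±24% by half-width.

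The larger-distance definition changes least, because it keeps the printed ±14%, ±22% and ±17%. The cost is the edit alone: accrual, the decision rule and the analyses are unchanged.

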## VII. RISKS AND DISCOMFORTS

It is not known whether the treatment with proton beam in this study will result in less effective anti-cancer therapy compared to conventional photon beam radiation therapy. However, based on our previous experience treating thousands of patients with other types of tumors with proton radiation therapy, there has been no decreased effectiveness in anti-cancer therapy compared to photon beam radiation therapy. While on the study, a patient is at risk for the side effects described below. There may also be other side effects that we cannot predict. Medications may be given to make side effects less serious and uncomfortable. These side effects generally go away days or weeks after radiation therapy is stopped, but in some cases side effects can be permanent.

The risks and discomforts of proton radiation are likely to be less than that of photon radiation. The side effects of radiation treatment can be broken down into two groups, acute and generally self-limited and late effects (often chronic). Acute side effects include skin reaction, fatigue, and possible decrease of blood counts. Additionally the acute side effects are related to the tissues being irradiated. If mucosal surfaces are irradiated, it can result in mucositis. This manifests itself as pain and denuding of the superficial surfaces of mucous membranes.

### **Side effects (all reversible) during radiation therapy or shortly after: (those that apply will be checked for you by the doctor on the consent form)**

PHYSICAL RISKS:	FREQUENCY
 Temporary hair loss in area being treated	common
 Skin reaction in radiation port	common
 Nausea and/or vomiting	occasional
 Diarrhea or change in bowel habits	occasional
 Loss of appetite and weight loss	common
 Fatigue	common
 Decrease in bone marrow cells	common
 Difficulty swallowing: can be painful enough to lead to hospitalization	occasional
 Irritation of the eye	common
 Sore mouth or throat	common
 Alterations of taste	occasional
 Inflammation of lung, liver or kidney	occasional
 Thrush	occasional
 Headache	common
 Dehydration	occasional

NON PHYSICAL RISKS:	FREQUENCY
 Inability to perform at school, job	common
 Need for Treatment break or delay in finishing treatments	uncommon

**Side Effects Occurring Months or Years After Radiation Therapy (can be irreversible): The doctor will check those boxes that apply on the consent form and circle the expected frequency**

PHYSICAL RISKS:	FREQUENCY
 Permanent hair loss	occasional
 New cancer or tumor due to radiation	uncommon, but serious
 Cataract or other eye dysfunction	uncommon to common
 Hearing loss	uncommon to common
 Diminished hormone production	common
 Bone or soft tissue growth abnormality	common
 Abnormal curvature of spinal column	uncommon
 Hypothyroidism	unknown
 Scarring/damage to esophagus	occasional
 Peptic ulcer formation in stomach	rare
 Scarring of bowel	rare
 Premature failure of ovaries	occasional
 Abnormal development of uterus	occasional
 Damage to spinal cord or brain tissue	rare, but serious
 Limb length discrepancy	uncommon to common

NON PHYSICAL RISKS:	FREQUENCY
 Deterioration in memory function	occasional
 Inability to have children	unknown
 Difficulty in school, job performance	uncommon

Standard diagnostic radiological tests (MRI) and plain films of the region and CT scans of the region may be used to follow this treatment and at subsequent follow-up visits.

Reproductive risks: Because radiation therapy can affect an unborn baby, you should not become pregnant or father a baby before or during radiation treatments. You should also not nurse your baby. You may be asked to do a pregnancy test before you begin your radiation treatments if there is a concern about being pregnant.

For more information about the risks and side effects, ask the investigator or your doctor.

## **VIII. POTENTIAL BENEFITS**

If a patient agrees to take part in this study, there may or may not be direct medical benefit to them. There is the potential benefit that protons will decrease some long-term

side effects. It is hoped that the information learned from this study will benefit other patients receiving radiation for rhabdomyosarcoma in the future.

## **IX. MONITORING AND QUALITY ASSURANCE**

### **Monitoring of data:**

Since proton beam radiation is a novel approach to treating pediatric rhabdomyosarcoma, and since toxicities are site specific, a monitoring rule is provided in the event of serious unexpected complications. Accrual will be suspended for a comprehensive review in the case of a non-cancer death or grade 4 (life-threatening) toxicity within 12 months following completion of radiation if it may be possibly related to radiation or another cause cannot be determined. The probability of one or more such event occurring among a total of 80 patients is more than 98% assuming the true rate were 5% or higher. If the underlying event rate were only 0.5%, the probability of suspension at any time throughout the accrual period is 33%.

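### The accrual-suspension rule opens at completion of radiation, so a possibly related life-threatening event during the course does not trigger it as written

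*Combined protocol and SAP*

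**What the plan says.** Section IX, Monitoring of data, gives the purpose of the rule: "a monitoring rule is provided in the event of serious unexpected complications". The trigger is one event: "Accrual will be suspended for a comprehensive review in the case of a non-cancer death or grade 4 (life-threatening) toxicity". The same sentence sets the window, "grade 4 (life-threatening) toxicity within 12 months following completion of radiation", and the attribution condition, "if it may be possibly related to radiation or another cause cannot be determined". The section then states the chance of at least one trigger among 80 patients as more than 98% at a true rate of 5% or higher, and as 33% at 0.5%.

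Section VI sets the outcomes: "Primary outcomes are acute and late complications following proton beam irradiation to the tumor or tumor bed". It defines the acute period so that it includes the course: "acute side effects are those occurring during radiotherapy or up to 90 days after the last dose". The current accrual goal in that section is 115.

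Three other places bear on events during the course:

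- Section IV, Acute Toxicity, has toxicity scored at weekly visits during radiation.
- Section IX, Reporting Adverse Events, requires a report to the principal investigator within 24 hours for death and for grade 4 acute toxicity, with myelosuppression excepted. It attaches no action on accrual.
- Section V, Treatment Delay, lets an individual patient's treatment be delayed after a serious adverse event. It too says nothing about accrual.

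**The concern.** The rule is there to halt enrolment and force a review when a novel treatment does unexpected serious harm. Its window opens only when radiation is completed. A possibly related grade 4 toxicity in the third week of treatment would be reported, but the rule would not call for suspension. On the natural reading of the sentence, the same holds for a non-cancer death during the course.

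The protocol names the radiation period where it means to include it, as in the acute definition in Section VI. The suspension rule has no such words. At stake is whether enrolment continues without a mandatory review after an event of exactly the kind the rule was written for, although the data needed to apply the rule are already collected every week.

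**Working it through.** **Which period each provision covers**

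| Provision | During radiation | After radiation | Acts on accrual |
|---|---|---|---|
| Acute outcome (Section VI) | yes | to 90 days after last dose | no |
| Weekly toxicity scoring (Section IV) | yes | at least one further score within 3 months | no |
| 24-hour report (Section IX) | yes | yes | no |
| Treatment delay (Section V) | yes | not applicable | no |
| Suspension rule (Section IX) | not as written | 12 months from completion | yes |

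Only the last row acts on accrual, and it is the only row about events that leaves out the course.

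**Length of the omitted period.** Section V gives typical doses of 36 to 50.4 Gy, 1.8-2.0 Gy per fraction, five fractions a week. Shortest: 36/2.0 = 18 fractions, 18/5 = 3.6 weeks. Longest: 50.4/1.8 = 28 fractions, 28/5 = 5.6 weeks.

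**The plan's own figures.** With independent patients, each observed for the whole window, P(at least one event) = 1 - (1 - p)^n.

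- n = 80, p = 0.05: 1 - 0.95^80 = 0.983 (stated: more than 98%).
- n = 80, p = 0.005: 1 - 0.995^80 = 0.330 (stated: 33%).

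Both reproduce. Here p is the rate of events that the rule counts, so these figures neither show nor hide the gap in the window.

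**Restated for the current goal of 115**

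- p = 0.05: 1 - 0.95^115 = 0.997.
- p = 0.005: 1 - 0.995^115 = 0.438.

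**Cost of including the radiation period.** The documents give no event rate for that period. Assume that it adds 0.5, 1 or 2 percentage points to the 0.5% rate.

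| Added (assumed) | Total p | n = 80 | n = 115 |
|---|---|---|---|
| 0 | 0.5% | 33.0% | 43.8% |
| 0.5 points | 1.0% | 55.3% | 68.5% |
| 1 point | 1.5% | 70.2% | 82.4% |
| 2 points | 2.5% | 86.8% | 94.6% |

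Since one event is enough, the chance of suspension is sensitive to even small additions.

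**The case against.** **The omission may be deliberate.** Section VI warns that concurrent chemotherapy may confound acute symptoms. Section VII lists a fall in marrow cells as common, and Section V mentions neutropenia needing admission under concurrent chemotherapy. The suspension rule lacks the myelosuppression exception found in the reporting list, so a widened window could fire on expected events. This objection stands as a cost, and the fix must deal with it. It does not justify the gap, because the plan gives no such reason and the attribution condition already screens out some of these events.

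**The wording allows other readings.** The 12-month phrase could limit only the toxicity, leaving deaths without any window, or could be meant only as an upper limit. Both are possible, so the exclusion of deaths is the natural reading and not a certainty. A rule triggered by one event should not depend on how its sentence is parsed.

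**On-treatment events are not unseen.** This is true: they are scored weekly and the serious ones are reported within 24 hours. But a report is not a suspension.

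A reader might also infer three stronger points that the documents do not support:

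- *That the 98% is overstated.* If half of all qualifying events fell during radiation, a 5% all-period rate would trigger the rule among 80 patients with probability 1 - 0.975^80 = 86.8%. That share is invented, and the calculation redefines the 5%, which the plan applies to events inside its own window. The figure is illustrative only.
- *That a patient whose course is stopped early is never covered.* Section VI uses completion of radiation and the last dose interchangeably, so the window may open at the last fraction given. This needs stating, but the exclusion is not shown.
- *That the study has no other suspension rule.* Appendix III, the Data and Safety Monitoring Plan, is listed in the contents but was not in the text available for this review. It may contain one.

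**Conclusion.** The point holds on the wording. In the text available, the only accrual-suspension rule counts grade 4 toxicity, and on the natural reading non-cancer death, from completion of radiation onwards. Possibly related events during the course, typically 3.6 to 5.6 weeks per patient, do not trigger it, although they belong to a primary outcome and are recorded weekly.

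There is no arithmetic error: 98% and 33% are right for 80 patients and for the events now counted. How much protection is lost cannot be calculated, because the documents give no on-treatment event rate. What can be calculated is that at 115 patients the trigger probabilities are 99.7% at a 5% rate and 43.8% at 0.5%, and that widening the window could raise the chance of suspension substantially under the assumed additions. This is a cheap improvement to the monitoring section, provided that the myelosuppression question is settled at the same time.

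**What to change.** 1. In Section IX, Monitoring of data, state that the window runs from the first fraction to 12 months after the last fraction, whether or not the course was completed, and that it applies to both non-cancer deaths and grade 4 toxicity.
2. Reconcile this with the acute definition in Section VI and the reporting list in Section IX. In particular, the sponsor should state whether the myelosuppression exception in the reporting list also applies to the suspension rule. Check Appendix III for consistency.
3. Restate the trigger probabilities for the chosen window and for 115 patients: 99.7% at 5% and 43.8% at 0.5%, where both rates now refer to all events from the first fraction. If the sponsor has an on-treatment rate from patients already enrolled, use it in place of the assumed additions.

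The cost is a few sentences and no new data collection. The price in conduct is more suspensions for review: 55-87% among 80 patients, against 33% now, if the radiation period adds 0.5 to 2 percentage points (assumed) to a 0.5% rate. How the exception is settled will affect where in that range, or outside it, the true figure lies.

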**Source of subjects and recruitment methods:**

Approximately 320 cases of pediatric rhabdomyosarcoma are diagnosed in the US per year[1]. Patients have been coming to MGH from all over the United States to be treated with proton irradiation and this trend is likely to continue. Patients will be recruited from MGH, BWH, Boston Children's Hospital, DFCI and MD Anderson Cancer Center. We estimate an annual accrual of 10 pediatric sarcoma patients across all participating sites, for a total accrual of 80 patients. Proton radiotherapy will be listed on the MGH Proton Center web site as a formal protocol and information of its availability will be made known to treating professionals through group (COG) meetings.

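### The accrual-suspension rule is still evaluated at 80 patients although accrual was revised to 115; the stated 33% chance of suspension at a 0.5% event rate becomes about 44%

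*Combined protocol and SAP*

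**What the plan says.** Section IX, Monitoring of data, sets the trigger: "Accrual will be suspended for a comprehensive review in the case of a non-cancer death or grade 4 (life-threatening) toxicity within 12 months". The months are counted from the end of radiation, and an event qualifies if a link to radiation is possible or no other cause can be found. One event is enough. Two properties of the rule follow. At a high event rate: "The probability of one or more such event occurring among a total of 80 patients is more than 98% assuming the true rate were 5%". The same sentence extends this to rates above 5%. At a low rate: "If the underlying event rate were only 0.5%, the probability of suspension at any time throughout the accrual period is 33"%.

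The documents give two accrual totals:

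- Section III, Source of subjects and recruitment methods, estimates 10 patients a year "for a total accrual of 80 patients".
- Section VI, Biostatistical Analysis, makes an allowance ("Allowing for 5% inflation for unevaluable patients due to ineligibility or early dropout") and on that basis sets the larger total: "the revised accrual goal is a total of 115 patients". It builds the late-effects decision rule on 110 patients, and later says that accrual was increased to improve the precision of tissue-specific toxicity estimates.

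All of this is current body text. None of it comes from a log of changes.

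**The concern.** Section VI calls 115 the revised goal, so 80 looks like a total from before the increase that was left in Sections III and IX. A rule triggered by one event fires more often as more patients are exposed, so its properties cannot carry over unchanged from 80 patients to 115. The low-rate figure is stated for the whole of accrual, and accrual now means 115 patients.

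This paragraph is the only place where the documents put numbers on a safety rule, and Section VI plans no formal sequential monitoring of efficacy. Anyone judging whether a one-event trigger is tolerable reads that a trial with a 0.5% event rate has a one-in-three chance of being suspended. If the true chance is appreciably higher, that judgement rests on a figure that flatters the design. The two totals also leave the intended enrolment unclear.

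**Working it through.** **Inputs**

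- Trigger: one qualifying event (Section IX).
- Event rates: p = 0.5% and p = 5% (Section IX).
- N = 80 (Sections III and IX); N = 115 enrolled and 110 in the decision rule (Section VI).
- Assumption: patients are independent with a common event probability. The plan's own figures imply the same.

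**Formula**

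P(at least one event) = 1 − (1 − p)^N

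**Step 1. Reproduce the plan's figures at N = 80**

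- p = 0.5%: 1 − 0.995^80 = 0.3304, stated as 33%.
- p = 5%: 1 − 0.95^80 = 0.9835, stated as more than 98%.

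Both reproduce. Solving in reverse, ln(1 − 0.33) / ln(1 − 0.005) = 79.9, so the 33% was computed for 80 patients.

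**Step 2. Apply the same formula to the revised accrual**

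| N | p = 0.5% | p = 5% |
|---|---|---|
| 80 | 33.0% | 98.3% |
| 110 | 42.4% | 99.7% |
| 115 | 43.8% | 99.7% |

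At p = 0.5% the change from 80 to 115 is 43.8 − 33.0 = 10.8 percentage points, or a third more in relative terms (0.4381 / 0.3304 = 1.33). A Poisson approximation gives 33.0% at 80 and 43.7% at 115, so the choice of formula does not matter. For the probability to be 33% with 115 patients, the event rate would have to be 1 − 0.67^(1/115) = 0.35%, not 0.5%.

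**Step 3. Check which total the design uses**

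- The decision rule in Section VI counts late effects among 110 patients, and 110 × 1.05 = 115.5, in line with a goal of 115.
- Section VI projects 56 parameningeal and 24 orbital patients, which already makes 80. It adds 3 to 6 patients at each of six rarer sites, a further 18 to 36, for a total of 98 to 116.

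Neither the decision rule nor the site projections can be met with 80 patients, so 115 is the operative total.

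**The case against.** The strongest reply is that the 33% is not a miscalculation. Section IX names its denominator and the arithmetic is right for it. That stands: the fault is a sample size that was not carried through.

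A second reply is that nothing done in the trial would change. The trigger is one event at either total, the result is a review rather than termination, detection at a 5% rate improves, and the plan sets no maximum suspension probability that 44% would exceed. This also stands. It limits the consequence to the description of the rule, but it does not make the description true.

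A third reply is that 44% is the top of a range. The event window runs to 12 months after radiation, so some events among the last enrolled would occur after accrual has closed. At an assumed 10 patients a year, about 115 − 10 = 105 patients would complete the window during accrual, and 1 − 0.995^105 = 40.9%. Using the 110 evaluable patients gives 42.4%. These are fair refinements, but neither comes near 33%. The plan's own calculation counts every patient, and the same window adjustment would lower its figure too: 1 − 0.995^70 = 29.6% for a trial of 80. The 5% allowance covers ineligibility and early dropout, and patients of either kind who are treated can still have a qualifying event. The like-for-like comparison is therefore 33.0% against 43.8%.

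Finally, the statement of more than 98% at a 5% rate does not fail. Rewording it is a matter of consistency.

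**Conclusion.** The concern holds. The 33% is wrong as written for the current design. By the plan's own method the chance of at least one suspension at a 0.5% event rate is 43.8% with 115 patients, and about 41% to 44% under the other reasonable denominators. The companion figure at a 5% rate remains true, at 99.7%. The result assumes a common, independent event probability and counts at least one suspension; the documents do not say whether the rule applies again after a review. The primary analysis is unaffected, because Section VI already uses 110 and 115. The point should be corrected because it misstates a property of the safety rule in the favourable direction and leaves two enrolment totals in force.

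**What to change.** In Section IX, replace 80 with 115, give the probability at a 5% rate as more than 99%, and give the probability of suspension at a 0.5% rate as about 44%. In Section III, change the total to 115 and confirm whether 10 patients a year is still the expected pace. If it is, accrual takes 115 / 10 = 11.5 years rather than 80 / 10 = 8.

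The cost is a few words in two places. No procedure, data item or analysis changes. The restated figure is less favourable, so the sponsor should confirm that a 44% chance of suspension at a 0.5% event rate was considered when the one-event trigger was kept for the larger trial.
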